The actual performance of the sTMS device in clinical practice is more likely to be reflected by the results of the PP analysis in the non-treatment naive population. These are the subjects who are most likely to seek sTMS treatment based upon the recommendation of their physicians. **Subjects who had attempted or completed prior antidepressant treatment in the current episode (ATHF 1 - 6) demonstrated significantly greater benefit from sTMS treatment compared to sham (-8.58 vs. -4.25, $p=0.005$), while treatment-naïve subjects (ATHF 0) showed no significant difference between active and sham (-9.76 vs. -10.08; $p=0.28$).** **Subjects who had attempted or completed prior antidepressant treatment in the current episode also had a statistically significantly higher response rate (34.2% vs. 8.3%, $p= 0.017$) and a numerically but not significantly higher remission rate (13.2% vs. 5.6%, $p=0.26$) with active treatment than with sham; treatment-naïve subjects showed the opposite pattern.** The magnitude of the improvement seen in this population is similar to or greater than that seen with medication and already-approved rTMS devices.

One conclusion from this study was that poor quality EEG recordings (i.e. high variability, poor electrode preparation) could result in the assignment of an inappropriate treatment IAF, and that patients treated at a frequency greater than 1 HZ from their IAF did not respond as well as those treated at the correct value. Consequently, NeoSync modified the NEST software to include an automatic EEG quality qualification process to improve the assignment of the correct treatment frequency. **The present study is designed to confirm that treatment with the modified software produces clinical improvement comparable to that demonstrated in the previous study in the non-treatment naive PP sub population.** Therefore, only patients who failed to respond to at least one AD medication in the current episode (i.e. treatment resistant) will be studied in this trial.

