5.4 OPEN LABEL FOLLOW-UP PHASE

Following completion of their treatment period, subjects who have not remitted (remission defined as a HAM-D₁₇ score ≤ 7) may be offered 6 weeks of open label sTMS treatment, if the clinician feels this is appropriate for that subject.

Subjects that enter the open label sTMS follow-up phase will continue to use their existing PPM. These PPMs will function in the open label device regardless of whether they were associated with an active or sham device for Weeks 1 through 6.

The open label sTMS device will deliver the same therapy as the active device does during the treatment phase. However, the device will look and sound different than either the active or sham to help maintain the blind.

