- Vital Signs (Heart Rate [HR], Blood Pressures [BP])
- Weight
- Pregnancy Test (HCG)
- Urine Toxicology Screen
- HAM-D/MADRS (Montgomery-Åsberg Depression Rating Scale)
- IDS-SR (Inventory of Depressive Symptomatology – Self Report)
- C-SSRS (Columbia Suicide Severity Rating Scale)
- Standard 12 lead ECG (optional)
- Physical Examination (optional)
- Laboratory Assessments (optional)

FOLLOW-UP VISITS

General Overview: The first treatment (Day 1) may occur on the same day as the baseline visit (Day 0) if all study criteria are met and randomization procedures are complete, or subjects will be asked to return on a subsequent day to begin the weekly treatment schedule. Subjects will come to the clinic for 5 daily treatment sessions per treatment week for a total of 30 treatment sessions over 6 treatment weeks. A consistent Monday through Friday weekly treatment schedule will be highly encouraged. However, a visit interval of 5-10 calendar days will be allowed for each treatment week to accommodate visit scheduling adjustments when needed. Treatment will be discontinued at the end of Week 6 (30 treatment sessions). Subjects will be clinically evaluated for safety and efficacy at the end of each of the six weekly treatment

courses. Subjects who have not remitted (remission defined as a HAM-D¹⁷ score of ≤ 7 (Zimmerman et al., 2004)) at the Week 6 evaluation visit may be eligible to receive open label sTMS during the six-week follow-up phase. If so, additional weekly treatment evaluation visits shall be performed at the end of treatment Week 7, 8, 9, 10, 11 and 12. Subjects who do not meet response criterion (relative to pretreatment baseline, Day 0) following 3 weeks (15 treatments) of open label treatment may be offered additional concomitant antidepressant therapy for the final 3 weeks of open label treatment.

Alternatively, if the clinician feels it is not appropriate for the subject to participate in the open label sTMS follow-up, the subject chooses not to participate in the open label follow-up or if the subject has remitted in the blinded phase, subject will be deemed to have completed participation in this study.

Specifics of the study visits are as follows:

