For the six-week double-blind phase, imputation of data on the primary endpoint will be performed as described below. For the six-week follow-up open-label phase (Weeks 6 – 12), all efficacy and safety summaries will be based on the all sTMS treated subject population, which consists of all subjects who have entered the six-week follow-up Phase. All efficacy analyses will be performed on the Observed Cases (OC) dataset only for each week in this open-label Phase. That is, no imputation will be used, and only data observed during the follow-up Phase will be summarized. Analyses in the open-label phase will be presented by double-blind

treatment group and for both treatment groups combined. Baseline for the double-blind phase will be defined as the last available value measured post-washout and prior to the first double-blind dosing. Baseline for the open-label phase will be defined as (a) the last post-washout assessment measured prior to the beginning of the double-blind treatment phase for patients randomized to sTMS in the double-blind phase; and (b) the last double-blind assessment measured prior to the beginning of the open-label phase for patients randomized to Sham in the double-blind phase.

Analysis of Primary Efficacy Endpoint

HAM-D/MDRS will be assessed at screening, baseline, Week 1-6 Evaluation Visits, and during the open-label phase through Week 12 evaluation visit. The primary efficacy endpoint is clinical response, defined by 50% or greater reduction on the HAM-D¹⁷ from baseline to Week 6. The efficacy analyses will be performed on the PP, ITT with available data, and ITT with imputed data (see below for imputation methods) analysis populations. The PP analysis population is the primary analysis population for efficacy per e-mail discussion between NeoSync and the FDA on July 17, 2015.

The null hypothesis is that the active sTMS treatment group does not differ from the sham group with respect to the proportion of patients with clinical response at Week 6. The corresponding alternative hypothesis is that the active sTMS treatment group differs from the sham group with respect to the proportion of patients with clinical response at Week 6.

Specifically, the primary efficacy analysis will be a test of the hypotheses:

$$H_0: \pi_A - \pi_S = 0$$

and

$$H_a: \pi_A - \pi_S \neq 0$$

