where π_A is the proportion of subjects who show 50% or greater improvement in mean HAM-D¹⁷ total score from baseline (Day 0) to Week 6 for the active treatment and π_S is the equivalent value for the sham-controlled group. The test of the null hypothesis will be based on Fisher's exact test at a two-sided 0.05 level of significance. In addition, the observed response rates and two-sided 95% confidence intervals of the risk difference between treatments will be presented, calculated using the Wilson method discussed in Newcombe (1998).

An assessment of treatment-by-investigative center interaction on the proportion of clinical responders at Week 6 will be carried out using the Breslow-Day test. Sites with fewer than 10 subjects in the PP group will be pooled with other centers by geographic region prior to carrying out analyses (the same pooled sites will then be used for the analyses on the ITT analysis population). The pooling will be carried out before the blind is broken. A 0.15 level of significance will be used to assess the interaction. A non-significant interaction or an interaction significant but only quantitative in nature will support the pooling of results across study centers for the final analysis.

For the six-week open-label follow-up phase, the proportion of patients with a clinical response at each open-label visit for each double-blind treatment and for both treatments combined will be presented. The proportion of patients with a clinical response at each visit will be compared between double-blind treatment in a similar manner as above. These open-label analyses are

considered exploratory.

INTERIM ANALYSES

Due to uncertainty regarding the expected sham response rate and resulting treatment effect differential, this study will utilize an adaptive design that allows one interim sample size re-estimation after a minimum of 70 subjects have been enrolled and completed 6 weeks of treatment (or dropped out prior to 6 weeks). The pre-specified maximum allowable adjusted sample size following re-estimation will be 240 randomized, or two times the initial planned sample size of 120 enrolled, based on practical resource constraints and the desire to achieve a minimum differential of 12% between active and sham response rates. The re-estimation of sample size will be conducted by an independent biostatistician following a pre-specified plan as described by Mehta and Pocock, 2010 and presented to the independent data monitoring board (DMB).

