For the six-week follow-up open-label phase, double-blind treatments will be compared on the above endpoints at Week 12 in a similar manner as described above. Here, baseline will be defined as the last post-washout assessment measured prior to the beginning of the double-blind treatment phase for patients randomized to sTMS in the double-blind phase; baseline will be defined as the last double-blind assessment measured prior to the beginning of the open-label phase for patients randomized to Sham in the double-blind phase. There will be no assessment of interactions with investigative site, nor will there be imputation of missing data.

I. Exploratory Analyses

Exploratory efficacy variables are listed below. Analyses comparing treatments on these variables will be carried out on the ITT and PP populations; there will be no imputation of missing data, and there will be no assessment of center-by-treatment interactions.

- Change from baseline in HAM-D¹⁷ score at each time point;
- Change from baseline in MADRS score at each time point;
- Remission at each visit, where remission is defined by a total score of ≤ 10 on the MADRS;
- Change from Baseline on the HAM-D¹⁷ subscale scores (Maier, anxiety, retardation and sleep) at each time point;

- Change from Baseline on the HAM-D²⁴ and HAM-D²⁸ at each time point;
- Clinical response (as defined above for HAM-D¹⁷) for HAM-D²⁴ and HAM-D²⁸ at each time point;
- Change from Baseline on the IDS-SR30 scale at each time point.

Change from Baseline on the HAM-D¹⁷, HAM-D²⁴ and HAM-D²⁸ scores, IDS-SR30 score, and MADRS score will be analyzed using analysis of covariance at each visit adjusting for the baseline value of the endpoint. Proportion of subjects with remission and with clinical response will be analyzed using Fisher's Exact test at each visit.

J. Safety Analysis

The assessment of safety will be based mainly on the frequency of adverse events recorded. Other safety data (e.g., vital signs and ECG) will not be collected systematically but will be considered as appropriate. All safety analyses will be performed on the Safety Population as defined above. Safety summaries will be performed for each of the active and Sham treatments.

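### The SAP tests the original arms against each other at open-label visits, although Week 6 remitters have left the study by then, so these are not comparisons of randomised groups

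*SAP*

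**What the plan says.** **Who leaves.** Protocol section 3 and the SAP's Follow-up Visits overview state the same rule: "if the subject has remitted in the blinded phase, subject will be deemed to have completed participation in this study". Protocol section 5.4 limits the open-label phase to subjects who have not remitted (remission being HAM-D17 of 7 or less). They "may be offered 6 weeks of open label sTMS treatment, if the clinician feels this is appropriate for that subject". After Week 6 the flowcharts in both documents list open-label visits only.

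**Who is analysed.** The SAP's General Overview of Methods says that the open-label population "consists of all subjects who have entered the six-week follow-up Phase" and that "no imputation will be used, and only data observed during the follow-up Phase will be summarized". Section H repeats the no-imputation rule for Week 12.

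**What is tested.** For HAM-D17 response at open-label visits, the Analysis of Primary Efficacy Endpoint section states: "The proportion of patients with a clinical response at each visit will be compared between double-blind treatment in a similar manner as above". The method there is Fisher's exact test, and the section calls these open-label analyses exploratory. Section H extends between-arm testing to HAM-D17 change, MADRS change and MADRS response at Week 12: "double-blind treatments will be compared on the above endpoints at Week 12 in a similar manner as described above". That paragraph is not labelled exploratory and stands under the label-considerations heading, but the gatekept list in the same section names Week 6 endpoints only.

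**Baselines.** The General Overview and section H give the arms different open-label baselines: the pre-treatment score for original sTMS, and the last double-blind score for original sham.

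**Protocol.** Section 11.1 plans open-label summaries on the combined entrant population. The between-arm tests appear only in the SAP.

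**The concern.** Comparing the original arms at Week 12 looks like a randomised comparison, but it is not one. Entry is decided by the Week 6 HAM-D17 score, which randomised treatment may have changed. Those removed are the subjects with the best Week 6 outcomes. If the device works, more of them come from sTMS. Nothing in either document carries their remission forward, counts them as responders or follows them to Week 12.

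A p-value from such a test could be taken as evidence that the sTMS effect lasts, or that sham subjects catch up once treated. The test cannot support either reading, because a difference (or its absence) may come from who was allowed to enter.

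**Working it through.** **Plan's own figure.** The SAP's 81% power for 34% vs 8% with 46 per arm reproduces with a continuity-corrected two-proportion formula (81.4%; full enumeration of Fisher's test gives 83.6%). The point does not depend on it. Only the 46 per arm is used below.

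**Inputs.**
- Week 6 remission, m: 13.2% sTMS and 5.6% sham, from the non-naive per-protocol cohort of the earlier trial (Protocol section 1.1, which reports "a numerically but not significantly higher remission rate (13.2% vs. 5.6%, $p=0.26$) with active treatment than with sham").
- True Week 12 response if everyone were counted, R: not in the documents. Assumed equal in both arms, 30% to 60%.
- Share of Week 6 remitters still responders at Week 12, h: not in the documents. Assumed 100%, 75% or 50%, the same in both arms.
- All non-remitters are taken to enter and to have a Week 12 score, on one common pre-treatment baseline.

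**Step 1: who is removed.** Baseline HAM-D17 must be at least 17, so a remitter has fallen by at least 10 points, or 10/17 = 59%. Every eligible remitter is therefore also a Week 6 responder. Expected removals per 46: 46 x 0.132 = 6.1 sTMS and 46 x 0.056 = 2.6 sham.

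**Step 2: effect before any open-label treatment.** In the earlier cohort, response was 34.2% vs 8.3%. Among non-remitters it becomes (34.2 - 13.2)/86.8 = 24.2% and (8.3 - 5.6)/94.4 = 2.9%. The difference falls from 25.9 to 21.3 points through selection alone.

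**Step 3: effect at Week 12.** Response among entrants = (R - h x m)/(1 - m). The difference between arms is then

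(R - h) x [0.132/0.868 - 0.056/0.944] = (R - h) x 0.0928.

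The true difference is zero throughout, so the values below are pure selection (sTMS minus sham, in points):

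| Remitters still responders (h) | R = 30% | R = 40% | R = 60% |
|---|---|---|---|
| 100% | -6.5 | -5.6 | -3.7 |
| 75% | -4.2 | -3.2 | -1.4 |
| 50% | -1.9 | -0.9 | +0.9 |

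The shift is zero when h equals R and changes sign when h falls below R.

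**Step 4: size against sampling error.** Entrants per arm are 46 x 0.868 = 39.9 and 46 x 0.944 = 43.4. For R = 40% and h = 100%, the entrant rates are 30.9% and 36.4%. The standard error is sqrt(0.309 x 0.691/39.9 + 0.364 x 0.636/43.4) = 10.3 points, so the shift is 5.6/10.3 = 0.5 standard error. At the extreme cell (19.4% vs 25.8%) the standard error is 9.1 points and the ratio is 0.7. All other cells but one are below 0.5.

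**Step 5: the arm-specific baselines.** Mean HAM-D17 changes in the earlier cohort were -8.58 and -4.25 (Protocol section 1.1). Suppose that remitters improved by x points, from 10 (the eligibility floor in Step 1) to 20 (assumed). The non-remitter mean change is (mean + m x x)/(1 - m).
- x = 10: -8.36 vs -3.91, difference -4.46.
- x = 20: -6.84 vs -3.32, difference -3.53.

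Against the full-cohort difference of -4.33, removing remitters moves the Week 6 contrast by -0.1 to +0.8 points (positive is against sTMS). Restarting the sham arm from its last double-blind score takes away the 3.3 to 3.9 points that sham non-remitters had already gained, which favours sTMS. This is on raw change. The planned baseline covariate would absorb part of it, by an amount that the documents do not allow one to compute.

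**The case against.** The strongest case on the other side is that little depends on these tests. The open-label response comparisons are labelled exploratory, the gatekept list stops at Week 6, and the open-label population is openly defined as those who entered. All of that stands, and it limits the weight of the point.

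Several stronger readings are tempting, and the documents do not support them:
- *A reader might infer that the planned tests are biased against sTMS.* Step 3 leans that way for most assumed values, but only on a common baseline. The SAP's baselines differ by arm and push towards sTMS, and the Step 3 sign itself reverses if fewer remitters sustain response than the overall Week 12 rate.
- *A reader might infer that remitters vanish without trace.* SAP section A already reports the number and percentage entering open label by original arm. What it lacks is the reason for not entering. The SAP's only remission analysis uses MADRS of 10 or less, whereas the gate is HAM-D17 of 7 or less.
- *A reader might take about a quarter as the expected loss,* because 31 of 120 per-protocol subjects in the earlier trial were not eligible for open label. That set included treatment-naive subjects, whom this trial excludes, and is not split by arm.

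It can also be said that labelling the Week 12 tests exploratory, with a caveat on entry, would be enough. That would reduce misreading, but it would still produce p-values without a randomised interpretation.

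**Conclusion.** The point holds as a matter of validity, with modest weight. The open-label between-arm tests condition on Week 6 non-remission and do not compare randomised groups, and no passage repairs this. A common baseline alone would not repair it either, since remitters would still have no score.

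The remitter effect on response runs from -6.5 to +0.9 points, about 0.5 standard error in the 40% case with full persistence and 0.7 at most with 46 per arm. These figures rest on the earlier trial's remission rates, whose difference was not significant (p = 0.26), and on assumed values for Week 12 response and persistence. They leave out non-remitters who are not offered open label or decline it, a second selection of unknown direction. Because of the arm-specific baselines, the net direction of the tests as written is not fixed.

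A reader might also infer, from the heading over the Week 12 paragraph, that a label claim or the study's alpha is at risk. It is not: the primary analysis and the three gatekept secondaries all use Week 6 data.

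**What to change.** 1. In the SAP's Analysis of Primary Efficacy Endpoint section and in section H, remove the between-arm tests for open-label visits and Week 12. Report open-label results descriptively within each original arm, among entrants, and state that entry is not randomised.

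2. Extend section A (Subject Disposition) with one table by original arm, with all ITT and all PP subjects as denominators and these rows:
   - HAM-D17 remission at Week 6 and exited;
   - entered and responded at Week 12, measured against the Day 0 pre-treatment baseline in both arms;
   - entered and did not respond at Week 12, on the same baseline;
   - entered but no Week 12 score;
   - did not enter for other reasons.

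Remitters then appear as what they are, and every subject is accounted for.

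The cost is SAP wording and one table from data already collected. No visit, eligibility rule or primary analysis changes. The downside is the loss of open-label p-values that lie outside the gatekept sequence.

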The first treatment (Day 1) may occur on the same day as the baseline visit (Day 0) if all study criteria are met and randomization procedures are complete, or subjects will be asked to return on a subsequent day to begin the weekly treatment schedule. Subjects will come to the clinic for 5 daily treatment sessions per treatment week for a total of 30 treatment sessions over 6 treatment weeks. A consistent Monday through Friday weekly treatment schedule will be highly encouraged. However, a visit interval of 5-10 calendar days will be allowed for each treatment week to accommodate visit scheduling adjustments when needed. Treatment will be discontinued at the end of Week 6 (30 treatment sessions). Subjects will be clinically evaluated for safety and efficacy at the end of each of the six weekly treatment courses. Subjects, who have not remitted at the Week 6 evaluation visit, may be eligible to receive open label sTMS during the follow-up phase. If so, additional weekly treatment evaluation visits shall be performed at the end of treatment Week 7, 8, 9, 10, 11 and 12. Subjects who do not meet response criterion (relative to pretreatment baseline, Day 0) following 3 weeks (15 treatments) of open label treatment may be offered additional concomitant antidepressant therapy for the final 3 weeks of open label treatment.

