11 STATISTICAL METHODS

11.1 POPULATION FOR ANALYSIS

The Intent-to-Treat (ITT) Population will consist of all subjects who are randomized to a study group.

The Per-Protocol (PP) Population is comprised of subjects who receive treatments according to the recommended protocol schedule without any major protocol violation. Major protocol violations include but are not limited to:

- Receiving treatments other than those specified in the study protocol.
- Treatments not administered according to study protocol.
 - Subjects cannot miss more than 1 dose in a treatment week and their weekly visit interval cannot exceed 10 calendar days. Any subject who misses more than 6 doses in the 6 week treatment period (maximum of 60 days) is not considered compliant with the treatment and will not be included in the analysis.
- Receiving concomitant medications that are not allowed per the study protocol.
- HAM-D₁₇ not available at Week 6.

The PP population analysis will serve as the primary analysis population.

The Safety Population will consist of all subjects who received at least one study treatment.

For the six-week open label phase, all efficacy and safety summaries will be based on the combined sTMS-treated subject population, which consists of all subjects who have entered the six-week open label phase. For the open-label phase, all efficacy analyses will be performed on the Observed Cases (OC) dataset only. That is, no imputation for missing data will be used, and only data observed during the follow-up phase will be summarized.

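### The open-label comparisons test the original arms against each other using a different baseline in each arm, which favours original sTMS if sham entrants improve by Week 6

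*SAP*

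**What the plan says.** The SAP sets the open-label baseline in its General Overview of Methods and repeats it in section H (Secondary Analyses for Label Considerations). For one arm it is "the last post-washout assessment measured prior to the beginning of the double-blind treatment phase for patients randomized to sTMS", that is, Day 0. For the other, "baseline will be defined as the last double-blind assessment measured prior to the beginning of the open-label phase for patients randomized to Sham", which is normally Week 6.

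Two sets of between-arm tests use this baseline:

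- SAP, Analysis of Primary Efficacy Endpoint: "The proportion of patients with a clinical response at each visit will be compared between double-blind treatment in a similar manner as above". This means Fisher's exact test on HAM-D17 response. The same paragraph also pools the arms: "the proportion of patients with a clinical response at each open-label visit for each double-blind treatment and for both treatments combined will be presented". It calls these open-label analyses exploratory.
- SAP, section H: "double-blind treatments will be compared on the above endpoints at Week 12 in a similar manner as described above". This means ANCOVA adjusted for baseline for HAM-D17 and MADRS change, and Fisher's exact test for MADRS response. This paragraph carries no exploratory label.

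Protocol 11.1 also works with a pooled group: "For the six-week open label phase, all efficacy and safety summaries will be based on the combined sTMS-treated subject population".

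Elsewhere the documents use one baseline for everyone. Protocol 7.1 and the SAP's Follow-up Visits section judge response after three open-label weeks against the pretreatment Day 0 score, whichever arm the subject came from.

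**The concern.** Measuring each arm from its first active sTMS treatment is a sensible description within an arm. It does not support a test between arms. At Week 12 the sTMS-origin arm is credited with change over the whole study, and the sham-origin arm only with change since the end of the double-blind phase. Any improvement on sham before Week 6 is removed from one side of the comparison.

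Two patients with the same Day 0 and Week 12 scores can therefore be classified differently. The pooled response rate mixes two definitions of response. A sham-origin patient can also meet the Day 0 response criterion used at open-label Week 3 and still be tabulated as a non-responder.

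The stake is a between-arm difference with a small p-value that comes from the baseline definition alone. It could be read as evidence that earlier or longer sTMS works better.

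**Working it through.** The documents give no figure for the open-label comparisons, so there is no stated result to reproduce.

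**Inputs**

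- Day 0 HAM-D17: mean 21.0, SD 3.3 (Protocol 1.1, feasibility study); minimum 17 (inclusion criterion).
- Sham change by Week 6: mean -4.25 (Protocol 1.1, prior trial, per-protocol non-naive subjects).
- SD of that change: 4.74 (Protocol 1.1, non-naive Completers, whose own mean was -4.59). The mean and SD come from different cohorts.
- Entry to open label: Week 6 score above 7 (Protocol 5.4).
- Week 12 means, SDs and correlations are assumptions, shown as ranges.

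**Step 1. Arithmetic on means**

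Sham mean at Week 6 = 21.0 - 4.25 = 16.75.

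- Response cut-off: 21.0/2 = 10.5 (sTMS) and 16.75/2 = 8.4 (sham).
- Week 12 score of 10: (21 - 10)/21 = 52% reduction, against (16.75 - 10)/16.75 = 40%.
- Week 12 mean of 12 in both arms: change is 12 - 21 = -9.0 against 12 - 16.75 = -4.75. The unadjusted difference is 4.25 points with no real difference.

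**Step 2. ANCOVA**

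Let b be the pooled within-arm slope of the Week 12 score on baseline, and D the sTMS baseline mean minus the sham baseline mean. The ANCOVA estimate is the difference in Week 12 means minus b × D. With equal Week 12 means and equal Day 0 means, it equals -b × (sham entrants' mean improvement by Week 6).

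Excluding remitters reduces that improvement from 4.25 to 3.87 points (simulation of 1,000,000 subjects: Day 0 = 17 + gamma; Week 6 = Day 0 + normal(-4.25, 4.74), floored at 0, scores above 7 kept). At slopes 0, 0.3, 0.5 and 0.7 the artefact is 0, -1.2, -1.9 and -2.7 points.

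**Step 3. Response**

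The same sham-origin subjects are scored twice with Week 12 values held fixed. Moving the baseline from Day 0 to Week 6 lowers HAM-D17 response by 9 to 21 percentage points over 24 scenarios (Week 12 mean 9, 11 or 13; SD 5 or 7; correlation with Week 6 of 0, 0.3, 0.5 or 0.7). At mean 11, SD 5 and correlation 0.5, response falls from 46% to 29%.

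**Step 4. Rejection rate under a true null**

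Both arms' entrants are drawn from the same joint distribution: Week 12 mean 11, SD 6, 40 per arm, 4,000 trials per setting, nominal 5% tests. The figure of 40 is illustrative: 46 × (1 - 0.132) = 39.9 and 46 × (1 - 0.056) = 43.4, using per-protocol numbers and prior-trial remission.

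| Week 6 to Week 12 correlation | ANCOVA, SAP rule | Fisher, SAP rule |
|---|---|---|
| 0 | 5% | 13% |
| 0.3 | 14% | 16% |
| 0.5 | 34% | 19% |
| 0.7 | 69% | 28% |

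With Day 0 in both arms, the rates are about 5% (ANCOVA) and 3% (Fisher). Repeat runs agree within about 3 percentage points. Over the same correlations, ANCOVA rejects 4%, 9%, 25% and 48% at 25 per arm, and 5%, 17%, 46% and 82% at 55 per arm.

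**Step 5. Sensitivity to the sham improvement**

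A second simulation used different assumptions: normal scores, no exclusion of remitters, Week 6 SD 5.5, Week 12 mean 12 and SD 6, 45 per arm, correlations 0 to 0.6.

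| Sham improvement by Week 6 | ANCOVA artefact (points) | Response, sTMS vs sham |
|---|---|---|
| 0 | none | equal within about 1 percentage point |
| 2 | 0 to -1.4 | about 40% vs 30-35% |
| 4.25 | 0 to -3.2 | 39-41% vs 23-29% |
| 6 | 0 to -4.4 | about 40% vs 18-25% |

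Under the Step 4 set-up with correlation 0.5, a mean sham worsening of 2 points reverses the ANCOVA artefact to about +1 point.

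**The case against.** The strongest reply concerns weight. The gatekept endpoints in section H are all at Week 6, so neither the primary test nor any label claim depends on these comparisons, and the open-label response analyses are called exploratory. Entry is optional and limited: "Following completion of their treatment period, subjects who have not remitted" may be offered treatment. Some entrants "may be offered additional concomitant antidepressant therapy for the final 3 weeks of open label treatment". The comparison would not be a randomized one even with a common baseline. All of this stands and limits the importance of the point. It does not justify leaving a known artefact in a stated test. The section H comparison also carries no exploratory label and sits under a heading about labelling, ahead of the separate Exploratory Analyses section.

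It can also be said that anchoring at first active treatment is coherent and openly stated. That is true within an arm; the fault is in the between-arm test and the pooled rate.

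ANCOVA removes the artefact only if the slope is zero. The Fisher tests have no adjustment, and they reject 13% of the time even at zero correlation.

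The number of entrants is uncertain. Section H covers ITT as well as per-protocol subjects, entry is optional and enrolment may rise, so 40 per arm is neither a cap nor a forecast. The rejection rates move with it; the artefact in points does not.

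Finally, the SAP paragraph on open-label HAM-D17 response does not restate a baseline, and the visit-level criterion uses Day 0. The General Overview definition is the more natural one to apply. Even if Day 0 were meant there, section H states the arm-specific rule explicitly for its own endpoints.

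**Conclusion.** The concern holds. As written, the SAP's open-label between-arm tests and pooled response rate rest on different baselines by arm, and they can show a difference when Week 12 scores are identical.

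The cut-off example needs only the two prior-study means. The wider figures (response lower by 9 to 21 percentage points, ANCOVA artefact of 0 to -2.7 points, inflated rejection rates) rest on assumed Week 12 distributions and on inputs from mixed prior cohorts. They isolate the effect of the baseline rule and do not predict this trial.

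The direction favours original sTMS if sham entrants improve on average by Week 6, as the prior trial suggests, and reverses if they worsen. The ANCOVA part vanishes at zero slope. MADRS is not sized because the documents give no MADRS means. The point should be corrected, but it does not threaten the primary or gatekept conclusions.

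**What to change.** - In the SAP's General Overview of Methods, Analysis of Primary Efficacy Endpoint and section H, use Day 0 as the baseline for both original arms in every between-arm or pooled open-label analysis of change or response, for HAM-D17 and MADRS. If the section I analyses at each time point (HAM-D24, HAM-D28, HAM-D17 subscales, IDS-SR) extend to open-label visits, apply the same rule there.
- Keep change from the start of active treatment (Week 6 for sham-origin patients) as a descriptive summary within each arm, with no between-arm test and no pooled rate.
- Label the section H Week 12 comparisons exploratory, as is already done for open-label HAM-D17 response.
- State that, even with a common baseline, the comparison is not randomized, because entrants are selected Week 6 non-remitters and may receive added antidepressants.

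The cost is SAP wording and one changed derivation in the open-label tables. No new data are needed, since HAM-D and MADRS are collected at baseline for every subject.
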